1.2.5.3. Safety Parameters

Safety evaluations performed during the study included physical examinations, measurement of vital signs, 12-lead electrocardiograms (ECGs), clinical laboratory evaluations including hematology, serum chemistry, coagulation, and urinalysis, and monitoring of adverse events (AEs) (including DLTs and treatment discontinuations due to toxicity), and concomitant medications.

Further details on the definitions and analysis methods for safety endpoints are provided in [Section 4.4](#).

2. PATIENT POPULATION

2.1. Population Definitions

The following patient populations will be evaluated and used for presentation and analysis of the data for all trial stages:

- Modified Intent-to-Treat (mITT) Population: All patients who are eligible based on the screening criteria who received at least 1 dose of tagraxofusp and are evaluable for efficacy (has an efficacy assessment after first treatment or discontinued due to death or progressive disease) prior to that time. Patients will be grouped according to the planned dose level at time of enrollment.
- Per-Protocol (PP) Population: All patients from the mITT population who are compliant with all major aspects of the protocol and have received at least 1 cycle of tagraxofusp (or treatment was delayed or patient discontinued treatment early due to safety finding related to study treatment). Patients will be grouped according to the planned dose level at time of enrollment.
- Immunogenicity Population: All patients enrolled in the study who received at least 1 dose of tagraxofusp and had at least 1 non-missing immunogenicity sample result.
- PK Population: All subjects who receive at least 1 dose of Tagraxofusp, have at least one plasma sample collected, and the corresponding plasma PK concentration is quantifiable.
- Safety Population: All patients enrolled in the study who received at least 1 dose of tagraxofusp. Patients will be grouped according to the actual dose level received.

The mITT population is the primary population for the analysis of efficacy parameters, and will be used to support baseline endpoints. The immunogenicity population will be used for summary of immunogenicity results. The PK population will be used for the analysis and summary of PK data. The Safety population is the primary population for the analysis of disposition, baseline, and safety endpoints. Patients included in the PP population or reasons for exclusion from the PP population will be identified in a data listing. Note that the intent-to-treat population, defined as all eligible patients, will not be used in any analyses.

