14.1 General Considerations

Analyses will be performed on all patients that received any quantity of tagraxofusp (i.e., all treated patients). The baseline value for a given variable is defined as the last measurement for the variable prior to the first infusion of tagraxofusp. Cycle 1 Day 1 for each individual patient is defined as the date the patient receives their first infusion of tagraxofusp.

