14.5 Analyses of Efficacy Data

Efficacy assessments include ORR, CR rate, specific components of the response criteria for each indication, duration of response (DOR), progression-free survival (PFS), and OS. Refer to [Appendix 18.1](#) for detailed response criteria established for CMML and MF. All efficacy outcomes will be presented by subgroups defined by disease.

Data from Stage 2 will be analyzed with descriptive statistical methods to provide estimates of rates of response. Stage 3A data will be analyzed with descriptive and correlation methods, with results intended to assist in the design of the confirmatory Stage 3B. Bayesian methods may also be used to determine likely values of response parameters, with Stage 2 results providing prior information for calculation of credible intervals based on Stage 3A data. Complete details of efficacy analyses will be provided in the Statistical Analysis Plan (SAP).

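### The SAP replaces the protocol's all-treated analysis set with an eligible-and-evaluable mITT set as primary for efficacy, does not record the change, and its evaluability condition can only raise ORR or leave it unchanged

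*SAP*

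**What the plan says.** Protocol 14.1 states: "Analyses will be performed on all patients that received any quantity of tagraxofusp (i.e., all treated patients"). The Statistical Methods part of the synopsis repeats it. No eligibility or evaluability condition is attached. Protocol 14.5 adds "Complete details of efficacy analyses will be provided in the Statistical Analysis Plan (SAP"), but does not withdraw 14.1.

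SAP 2.1 defines the mITT population as "All patients who are eligible based on the screening criteria who received at least 1 dose of tagraxofusp and are evaluable for efficacy". Evaluable means that the patient "has an efficacy assessment after first treatment or discontinued due to death or progressive disease". The same section says "The mITT population is the primary population for the analysis of efficacy parameters", and SAP 4.3 runs the efficacy analyses on mITT at 12 µg/kg/day, with the Safety Population (all treated) as supportive.

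The two sets also assign dose differently. For mITT, "Patients will be grouped according to the planned dose level at time of enrollment"; for Safety, "Patients will be grouped according to the actual dose level received". For the per-protocol set, "reasons for exclusion from the PP population will be identified in a data listing"; there is no matching commitment for mITT.

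SAP 1.2.5.1 names investigator-assessed ORR (CR or PR) as the primary efficacy endpoint. SAP Section 5 records the dropped MF sub-population, interim, Bayesian and correlative analyses, and several additions. It says nothing about the analysis population. The revision history in Section 9 does not list Section 2.1 either.

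**The concern.** In a single-arm study the denominator of the response rate determines both the estimate and its interval, so the choice of analysis set is a substantive part of the primary endpoint. The protocol and SAP disagree on that set, and a reader comparing them finds no explanation.

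The exclusion is also selective. Patients who die or progress stay in mITT. Those who can leave it on evaluability are treated patients who stopped for something else, such as toxicity, withdrawal of consent or the investigator's decision, before any efficacy assessment. Stopping early for toxicity is a result of treatment and belongs in the headline rate as non-response.

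**Working it through.** **Plan's own figures.** The documents give no number for this point. The one operating characteristic stated for Stage 3A (10 patients, true rate 0.15, 80% chance of at least one response) reproduces as 1 − 0.85^10 = 0.803, but it does not bear on the choice of population.

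**Direction of the evaluability condition.** Let N be the treated patients, r the responders, and k those dropped for having no post-treatment efficacy assessment and not having stopped for death or progression. A CR or PR requires an assessment, so none of the k can be a responder and r does not change:

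- all treated: ORR = r/N
- evaluable only: ORR = r/(N − k)
- ratio: N/(N − k) ≥ 1, so ORR rises whenever k > 0 and r > 0, and is otherwise unchanged.

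Enumerating every combination up to N = 60 gave 0 cases lower, 3,660 equal and 35,990 higher.

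**Direction of the eligibility condition.** This one has no fixed sign. Starting from 2/20 = 10.0%, removing one ineligible non-responder gives 2/19 = 10.5%; removing one ineligible responder gives 1/19 = 5.3% (0.1 to 26.0). The one-way statement therefore applies to evaluability alone, not to mITT as a whole.

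**Do other SAP rules bring these patients back?** SAP 4.3.1 has a not-evaluable category for best response, and SAP 3.10 keeps missing results in the denominator. Both operate inside the analysed population. When that population is mITT, a patient excluded from it is not reached by either rule.

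**Size.** k is not given, so it is an assumption, shown here from 0 to 4. N = 20 is the target for a Stage 3A cohort (SAP 3.1.2), and N = 30 is the extended Stage 2 cohort size (SAP 1.1.2). Neither is an actual analysis denominator: Stage 3A enrollment was stopped (SAP Section 5), and SAP 3.5 splits the tables further.

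| N | k=0 | k=1 | k=2 | k=3 | k=4 |
|---|---|---|---|---|---|
| 20 | ×1.000 | ×1.053 | ×1.111 | ×1.176 | ×1.250 |
| 30 | ×1.000 | ×1.034 | ×1.071 | ×1.111 | ×1.154 |

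With an assumed all-treated ORR of 10% and exact (Clopper-Pearson) 95% intervals:

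| Start | k=0 | k=1 | k=4 |
|---|---|---|---|
| 2/20 | 10.0% (1.2–31.7) | 2/19 = 10.5% (1.3–33.1) | 2/16 = 12.5% (1.6–38.3) |
| 3/30 | 10.0% (2.1–26.5) | 3/29 = 10.3% (2.2–27.4) | 3/26 = 11.5% (2.4–30.2) |

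The largest shift shown is 2.5 percentage points, against an interval about 30 points wide.

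**The case against.** The strongest reply is that little is lost. Protocol 14.1 is a general statement that names no primary efficacy set, and 14.5 hands the efficacy details to the SAP. The all-treated efficacy analysis is still planned (SAP 4.3). SAP 4.1 tabulates the number in each population and lists populations by patient. Reasons for exclusion should be largely recoverable from the listings of withdrawals (4.1), protocol violations (2.2) and efficacy data (4.3). Few patients may be dropped: Protocol Table 4 asks for End-of-Treatment marrow and imaging even in early stoppers, and its footnote 7 treats end-of-cycle hematology as serving efficacy. The analysis is descriptive, and Stage 3B will not start. Finally, the sponsor has already reviewed efficacy data, so relabelling the primary set now could itself look data-driven.

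Much of this stands, and it limits the harm. The silence of the Version 2.0 revision history is also weak evidence, because mITT may already have been in the previous SAP version; the silence of Section 5 is what counts.

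Three things do not fall. Delegating details does not cancel a stated population. Reporting the all-treated ORR as supportive does not change which estimate is called primary. And returning to the set that the protocol already names is not a new choice made from the data.

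**Conclusion.** The point holds. The SAP's primary efficacy population departs from Protocol 14.1, and Section 5 does not record it. The evaluability condition removes only treated patients who cannot be responders, so its effect on ORR is upward or nil; the eligibility condition may offset or add to that.

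The size is unknown. It is nil if no one is dropped. At the planned cohort sizes, with one to four patients dropped, the multiplier is 1.05 to 1.25 for 20 patients and 1.03 to 1.15 for 30. These figures rest on assumed values of k and an assumed 10% response rate, and the shifts are small against the exact intervals. No decision in the current plan depends on them. It should be fixed because ORR is the primary efficacy endpoint and the correction is cheap, not because the conclusions are at risk.

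**What to change.** In SAP 2.1 and 4.3:

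- Make all patients treated at 12 mcg/kg (Safety Population) primary for ORR, as in Protocol 14.1.
- Count a treated patient with no post-baseline response assessment as not evaluable for best response and as a non-responder.
- Keep mITT as supportive, and list the reason for each exclusion from it.
- State whether efficacy tables group by planned or actual dose, since the two populations differ on this.
- Record any remaining departure from Protocol 14.1 in SAP Section 5.

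Two smaller repairs belong in the same edit: say whether hematology alone counts as an efficacy assessment, and correct the bracket in the mITT definition, which seems to close before the final phrase that belongs inside it.

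The cost is mostly wording, because the Safety Population efficacy analysis at this dose is already planned. The headline ORR may come out slightly lower, and any patient whose planned and actual doses differ may change dose group.

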2.2. Protocol Violations

At the discretion of the Sponsor, major protocol violations, as determined by a review of the data prior to database lock and the conduct of statistical analyses, may result in the removal of a patient's data from the PP population. The Sponsor or designee will be responsible for producing the final protocol violation file (formatted as a Microsoft Excel file), in collaboration with Veristat and the data monitoring group as applicable; this file will include a description of the protocol violation and clearly identify whether or not this violation warrants exclusion from the PP population. This file will be finalized prior to database lock for any interim and final analyses.

All protocol violations will be presented in a data listing.

3. GENERAL STATISTICAL METHODS

3.1. Sample Size Justification

3.1.1. Stage 2 Sample Size Justification

An objective of Stage 2 is a preliminary assessment of response rates associated with tagraxofusp in CMML and MF. Because available anti-cancer agents are associated with very limited responses in the MPNs evaluated in this study, it is anticipated that an agent that confers a response rate $\geq 10\%$ may be considered active and worthy of additional investigation.

Initially, a sample size of 18 patients with a particular MPN (CMML or MF) was planned for enrollment in Stage 2. Furthermore, it was planned that in settings where there is evidence that a sufficient proportion of patients have experienced improvement in components of the response criteria, that additional investigation of tagraxofusp in a given MPN (CMML or MF) may have been considered appropriate based on preliminary data.

[figure not shown]
In order to ensure continued access to tagraxofusp in a controlled clinical study setting while additional investigations are being designed, the sample size in Stage 2 was increased by approximately 20-25 additional patients with MF in order to allow investigation of tagraxofusp in patients with MF and monocytosis and/or other emerging biological features that could help characterize the disease. Thus, across all study stages, approximately 50-55 patients with MF were planned to be enrolled.

3.1.2. Stage 3A Sample Size Justification

Approximately 20 patients with CMML may be enrolled in each of the two cohorts in Stage 3A to ensure a sufficient number of patients with specific baseline disease characteristics are enrolled to reject a meaningless rate of clinical activity in subsets of interest. (For our purposes, a meaningless rate will be taken to mean that there are no responders, using the definitions below, in the sample for each of the following subsets.) No formal stratification will be performed; however approximately 8-10 patients with baseline splenomegaly (defined as ≥ 5 cm below the left costal margin) and approximately 8-10 patients who are transfusion-dependent at baseline (receipt of at least 4 transfusions within 8 weeks before the first tagraxofusp dose) will be included in each 20-patient cohort. This intended enrollment distribution may be adjusted, depending on the actual prevalence of splenomegaly and transfusion-dependence seen in the general patient population as the study continues to enroll.

In this exploratory stage, the primary evidence of activity in each subset would be (1) a reduction in spleen volume that correlates with an improvement in symptom score or (2) conversion from transfusion-dependent to transfusion-independent. These occurrences on a per-patient basis would be considered responses within each subgroup. Clinical activity would have been demonstrated if at least 1 patient achieves either of these clinically important outcome responses. Up to 5 additional patients with either of these specific baseline characteristics may be enrolled in Stage 3A, to increase the confidence in the observed results, if necessary. It can be seen in the graph below that for any true rate of response that is ≥ 0.15 , this approach would have at least 80% power to detect at least one responder. Given at least a single responder, additional methods such as confidence interval estimation or formal power calculations, may be used.

The operating characteristics of this approach to sample size estimation in Stage 3A may be seen in the following graph. This graph presents the sample size required to have either an 80%, 90%, or 95% probability of at least 1 responder when the sample size is N, and the true probability of response is P.

As an example, if the true response probability were 0.15, 10 patients evaluated for a given response type would result in at least one response with 80% probability.

3.2. General Methods

All data listings that contain an evaluation date will contain a relative study day (Rel Day). Pre-treatment and on-treatment study days are numbered relative to the day of the first dose of study medication which is designated as Rel Day 1. The preceding day is Rel Day -1, the day before that is Rel Day -2, etc. The last day of study medication is designated with an "L" (e.g., Rel Day 14L). Post-treatment study days are numbered relative to the last dose and are designated as Rel Day 1P, Rel Day 2P, etc.

All output will be incorporated into Microsoft Rich Text File or Excel files, or Adobe Acrobat PDF files, sorted and labeled according to the International Conference on Harmonisation (ICH) recommendations, and formatted to the appropriate page size(s).

Tabulations will be produced for appropriate demographic, baseline, efficacy, safety, and immunogenicity parameters. For categorical variables, summary tabulations of the number and percentage of patients within each category (with a category for missing data) of the parameter will be presented. Two-sided 95% confidence intervals (CIs) will be computed using the Clopper Exact method. For continuous variables, the number of patients, mean, median, standard deviation, minimum, and maximum values will be presented. Time-to-event data will be summarized using Kaplan-Meier methodology using 25th, 50th (median), and 75th percentiles with associated 2-sided 95% CIs, as well as percentage of censored observations.

3.3. Computing Environment

All descriptive statistical analyses will be performed using SAS statistical software Version 9.4, unless otherwise noted. Medical history and adverse events (AEs) will be coded using the Medical Dictionary for Regulatory Activities (MedDRA) Version 19.0. Concomitant medications will be coded using the World Health Organization (WHO) Drug Dictionary (September 2016).

3.4. Baseline Definitions

For all analyses, baseline will be defined as the most recent measurement prior to the first administration of study drug.

3.5. Methods of Pooling Data

Disposition, baseline, and safety summaries will be displayed by dose as well as by disease and trial stage. Tabulations presented by dose will include a summary of each dose level for MF and for CMML separately.

7 µg/kg/day	9 µg/kg/day	12 µg/kg/day	Overall
-------------	-------------	--------------	---------

Tabulations presented by disease and trial stage will include a summary of each stage for MF (Stages 1 and 2) and for CMML (Stages 1, 2, and 3A).

MF			CMML			
Stage 1 (N=xx)	Stage 2 (N=xx)	Overall (N=xx)	Stage 1 (N=xx)	Stage 2 (N=xx)	Stage 3A (N=xx)	Overall (N=xx)

For myelofibrosis patients, summaries will be displayed by Dynamic International Prognostic Scoring System (DIPSS)-Plus Risk for treatment naïve and for relapsed/refractory patients separately.

Intermediate-1	Intermediate-2	High	Overall
----------------	----------------	------	---------

For chronic myelomonocytic leukemia patients, summaries will be displayed by CMML Type for treatment naïve and for relapsed/refractory patients separately.

CMMI-1	CMMI-2	Overall
--------	--------	---------

One patient with SM was treated in Stage 2 and will be presented in data listings. No patients with PED were treated so no separate tabulations or listings will be presented.

Summaries of efficacy results will be displayed separately for MF and CMML patient groups treated at 12 µg/kg, and separately for patients treated at 7 or 9 µg/kg. Efficacy results for MF patients will be presented separately for treatment-naïve and relapsed/refractory patients. For myelofibrosis patients, summaries will be displayed by DIPSS-Plus Risk for treatment naïve and for relapsed/refractory patients separately. For chronic myelomonocytic leukemia patients, summaries will be displayed by CMML Type for treatment naïve and for relapsed/refractory patients separately.

Treatment Naïve (N=xx)	Relapsed/ Refractory (N=xx)	Overall (N=xx)
---------------------------	--------------------------------	-------------------

Efficacy summaries of investigator report response data for CMML patients will be presented separately for treatment-naïve and relapsed/refractory patients, with Stages 1 and 2 presented separately from Stage 3A patients.

Stages 1-2			Stage 3A		
Treatment	Relapsed/ Refractory	Overall	Treatment	Relapsed/ Refractory	Overall
Naïve (N=xx)	(N=xx)	(N=xx)	Naïve (N=xx)	(N=xx)	(N=xx)

Summaries of immunogenicity results will be presented by dose, separated by disease for patients treated at 12 µg/kg/day.

7 and 9 µg/kg/day	MF 12 µg/kg/day	CMML 12 µg/kg/day	Overall 12 µg/kg/day	Overall
----------------------	--------------------	----------------------	-------------------------	---------

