18 Premedications administered 60 minutes (± 15 minutes) before tagraxofusp treatment: Diphenhydramine 50 mg IV (or an equivalent dose of another H1-histamine antagonist); acetaminophen 650 mg orally (or equivalent dose of paracetamol); methylprednisolone 50 mg IV (or an equivalent dose of another corticosteroid); famotidine 20 mg IV (or an equivalent dose of another H2-histamine antagonist).

19 Following treatment with premedication, tagraxofusp will be administered as a 15-minute infusion once daily for the first 3 consecutive days of a 21-day cycle. Individual tagraxofusp infusions may be delayed to allow for toxicity resolution, but all 3 infusions should be completed within 10 days.

20 Patients with MF should complete the MPN-SAF TSS (10-question evaluation concerning symptoms/well-being during the prior week) during screening and in every treatment cycle, prior to receiving therapy on the subsequent cycle. The MPN-SAF TSS should also be completed at End of Treatment.

21 Tumor assessments are to be performed during screening, at the end of C1 and C4, then every 12 weeks (± 7 days) and at End of Treatment. These include the IWG-MRT/ELN 2013 consensus report for MF and the IWG MDS 2016 consensus report for CMMI. These are detailed in [Section 11.12](#) and [Section 18.1](#).

Table 3: Stage 2: Study Events Schedule for Cycle 5 and Beyond in Stage 2

Procedures	Cycle 5 and Beyond			Safety: Through 30 Days After Last Infusion
	Days 1-3 (Up to Day 10 if Infusion(s) Held) Tagraxofusp Treatment		Cycles 5 and Beyond ² 12 Weeks (i.e., every 3 cycles) ±7 Days	
	Pre-Infusion	Infusion	End of Cycle ¹	
Concomitant medications/therapies	X	X		X
AE and SAE monitoring	X	X		X
ECOG performance status		X		X
Physical examination including assessment of hepatomegaly and splenomegaly		X		X
Vital signs and weight ³	X	X		X
Hematology ⁴	X	X		X
Serum chemistry ⁵	X	X		X
Coagulation parameters: PT/TNR, aPTT ⁶	X	X		X
Urinalysis ⁷		X		X
Peripheral blood for flow cytometry (Infusion 1)	X			X
Bone marrow aspiration/biopsy ⁸				X ⁹
MRI or CT scan of abdomen ¹⁰				X ⁹
Immunogenicity sampling ¹¹		X		X
Cytogenetic and molecular genetic testing				X
Administration of premedications ¹³	X			X
Administration of Tagraxofusp ¹⁴		X		X
MPN-SAF TSS evaluation ¹⁵		X		X
Vision assessment		X		X
Tumor response assessment ¹⁶			X ¹⁰	X

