14.2 Determination of Sample Size

14.2.1 Stage 2 (Patients with CMML Previously Enrolled and Patients with MF)

An objective of Stage 2 is a preliminary assessment of response rates associated with tagraxofusp in CMML and MF. Because available anti-cancer agents are associated with very limited responses in the MPNs evaluated in this study, it is anticipated that an agent that confers a response rate $\geq 10\%$ may be considered active and worthy of additional investigation.

Initially, a sample size of 18 patients with a particular MPN was planned for enrollment in Stage 2. Furthermore, it was planned that in settings where there is evidence that a sufficient proportion of patients have experienced improvement in components of the response criteria, that additional investigation of tagraxofusp in a given MPN may have been considered appropriate based on preliminary data.

Preliminary evidence of activity has been observed in patients with relapsed and/or refractory CMML and MF.

As of July 2021, 36 patients have been enrolled, comprising 20 patients with CMML-1 and 16 with CMML-2; median age was 69 years (range 42–81), and 75% of patients were male. Twenty-three patients (64%) had either high- or intermediate-risk genetics based on CPSS,

GFM, MMM, or ELN risk stratification systems. Prior therapies included HMA in 16 patients (43%), allogeneic stem cell transplantation (allo-SCT) in 3 (8%), and other in 12 (32%); 7 patients (19%) were high-risk and treatment naive. Overall, 16 patients (44%) had baseline palpable splenomegaly; in 12 of these patients, spleen size was ≥ 5 cm below left costal margin. Overall, 4 of 36 (11%) patients achieved bone marrow morphological complete responses (BMCRs), 1 of whom was bridged to allo-SCT; all 4 patients had splenomegaly at baseline. It is noteworthy that 2 of the 4 BMCRs, were observed in patients with high-risk genetic features. Fifteen patients (42%) with baseline splenomegaly had spleen responses; 9 patients (60%) had a $\geq 50\%$ reduction in spleen size, including 5 (42%) with splenomegaly of ≥ 5 cm at baseline.

[figure not shown]

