14.2.2 Stage 3A in Patients with CMML

The purpose of Stage 3A is to evaluate the clinical benefit derived from individual components, or variations thereof, of the MDS/MPN 2015 criteria that may allow for a prospective definition of a primary efficacy endpoint, that will provide the primary evidence of efficacy for regulatory decision-making in the planned confirmatory cohort (Stage 3B; to be added under the auspices of separate amendment). Individual evaluations will be performed for each of the two CMML cohorts in Stage 3A.

Approximately 20 patients with CMML may be enrolled in each of the two cohorts in Stage 3A to ensure a sufficient number of patients with specific baseline disease characteristics are enrolled to reject a meaningless rate of clinical activity in subsets of interest. (For our purposes, a meaningless rate will be taken to mean that there are no responders, using the definitions below, in the sample for each of the following subsets.) No formal stratification will be performed; however approximately 8-10 patients with baseline splenomegaly (defined as ≥ 5 cm below the left costal margin) and approximately 8-10 patients who are transfusion-dependent at baseline (receipt of at least 4 transfusions within 8 weeks before the first tagraxofusp dose) will be included in each 20-patient cohort. This intended enrollment distribution may be adjusted, depending on the actual prevalence of splenomegaly and transfusion-dependence seen in the general patient population as the study continues to enroll.

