4.3.7. Other Assessments of Disease Response

The proportion of subjects with $\geq 35\%$ reduction in spleen size from baseline and $\geq 50\%$ reduction in score from baseline will be summarized over time. The proportion of subjects with an anemia response for MF patients and with erythroid response for CMML patients will also be summarized over time.

For patients who were transfusion-dependent at baseline, the number and percentage of patients who achieved transfusion independence following treatment start will be summarized for any 12-week period (at any time, at C4D21-12 weeks and C7D28-24 weeks). Transfusion dependency will be for pRBCs, platelets, and both, as defined in [Section 1.2.5.1](#). The rate of transfusions will also be summarized at any time post-baseline, from pre-baseline to baseline, from baseline to Week 12, and from Week 12 to Week 24.

For patients who were Red Blood Cell Transfusion Independent at Baseline, the number and percentage of patients becoming transfusion dependent following treatment start will be summarized for any 12-week period (at any time, at C4D21-12 weeks and C7D28-24 weeks). Transfusion dependency will be summarized pRBC as defined in Section 1.2.5.1.

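### The SAP's CMML layout gives no Stage 3A column to the spleen-with-symptom and transfusion summaries on which Stage 3A was sized

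*SAP*

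**What the plan says.** **What was sized.** SAP 3.1.2 and Protocol 14.2.2 plan about 20 patients in each of two CMML cohorts. Each cohort is to include roughly 8 to 10 patients with baseline splenomegaly (at least 5 cm below the left costal margin) and 8 to 10 who are transfusion-dependent. A response is a spleen volume reduction that goes with symptom improvement, or conversion to transfusion independence. One responder is enough to show activity. The operating characteristic is stated as "10 patients evaluated for a given response type would result in at least one response with 80% probability", for a true rate of 0.15. On the unit of analysis, Protocol 14.2.2 says: "Individual evaluations will be performed for each of the two CMML cohorts in Stage 3A".

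**What is tabulated.** SAP 4.3 sends all efficacy summaries to SAP 3.5 for their layout. The general rule there is "Summaries of efficacy results will be displayed separately for MF and CMML patient groups treated at 12" µg/kg, followed by CMML type within prior-treatment group and by a Treatment Naïve, Relapsed/Refractory, Overall column set. None of these has a stage column. A separate sentence then covers one kind of output: "Efficacy summaries of investigator report response data for CMML patients will be presented separately" for the two prior-treatment groups, with Stages 1-2 set apart from Stage 3A.

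**The summaries concerned.** These are spleen volume (SAP 4.3.5), symptom score (4.3.6), and the joint spleen-and-score rate and transfusion conversion (4.3.7). For the joint rate, SAP 4.3.7 says only that the proportion with at least 35% spleen reduction and at least 50% "reduction in score from baseline will be summarized over time". It names no stage and no baseline-splenomegaly denominator.

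**The concern.** The outcomes that justify the Stage 3A sample size are the ones that lose the stage split. Baseline and safety tables have stage columns, and so do investigator-reported responses, but the measurement-based spleen, symptom and transfusion summaries do not. SAP 3.7 describes Stages 1 and 2 as generating hypotheses and makes evaluation of the individual response components the Stage 3A endpoint. A table that mixes the stages does not answer the question Stage 3A was set up to answer.

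Mixing could mislead in either direction. Earlier patients who can meet a definition could supply the responder. Earlier patients who cannot meet it, for want of a measurement, would lower the displayed rate, because SAP 3.10 takes percentages from the total population including patients with missing results.

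**Working it through.** **1. Reproduce the plan's figure.** Inputs are n = 10, p = 0.15 and at least 1 responder (SAP 3.1.2). The formula is P = 1 − (1 − p)^n.

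- n = 10: 1 − 0.85^10 = 80.3%, which agrees with the stated 80%.
- At the lower planned subset sizes, n = 9 gives 76.8% and n = 8 gives 72.8%.

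The figure describes one subset in one Stage 3A cohort. Tabulating by Stage 3A cohort leaves it unchanged.

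**2. Trace each CMML summary to its columns.**

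| Summary | Source | Stage split under SAP 3.5 |
|---|---|---|
| Objective response | SAP 4.3.1 | Yes, as investigator-reported data |
| Erythroid, platelet, neutrophil, spleen, symptom responses | SAP 4.3.1 | Possibly, if counted as investigator-reported |
| Spleen volume by MRI/CT | SAP 4.3.5 | None stated |
| Symptom score | SAP 4.3.6 | None stated |
| Joint spleen-and-score | SAP 4.3.7 | None stated |
| Transfusion conversion | SAP 4.3.7 | None stated |

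SAP section 5 lists changes to the planned analyses. Combining stages for these endpoints is not among them.

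**3. Illustration: earlier patients who can respond.** Let m earlier patients share a cell with 10 Stage 3A patients, all with p = 0.15. I take m from 0 to 12 because Protocol 14.2.1 reports 12 of 36 CMML patients with a spleen of at least 5 cm. Neither their stage nor their prior-treatment split is given, so the range is an assumption. P = 1 − 0.85^(10 + m):

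| m | P(at least 1 responder) |
|---|---|
| 0 | 80.3% |
| 3 | 87.9% |
| 6 | 92.6% |
| 9 | 95.4% |
| 12 | 97.2% |

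The true rate that gives 80% is 1 − 0.2^(1/(10 + m)), which falls from 0.149 at m = 0 to 0.071 at m = 12.

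**4. Illustration: earlier patients who cannot respond.** Suppose instead that the m earlier patients have no symptom score and stay in the joint denominator. A true 15% joint rate in 10 Stage 3A patients displays as 0.15 × 10 / (10 + m):

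- m = 6: 1.5/16 = 9.4%
- m = 12: 1.5/22 = 6.8%

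Steps 3 and 4 rest on opposite assumptions about the same patients. For the joint endpoint they are alternatives, not effects to be added.

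**5. Precision after separation.** The exact (Clopper-Pearson) 95% interval for 1 of 10 is 0.3% to 44.5%. For 1 of 8 it is 0.3% to 52.7%.

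**The case against.** The strongest reply is that pooling is inferred. No sentence in the SAP says that 4.3.5 to 4.3.7 combine the stages, and the table shells are in a separate document (SAP section 9). That is fair. Still, SAP 3.5 is the section on pooling, 4.3 defers to it, and its stage split is attached to one named kind of output. As written, the other outputs have no stage column.

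Some Stage 3A counts may also be available elsewhere. The 4.3.1 component responses include transfusion independence, within the erythroid and platelet definitions of SAP Table 8-4, and may already be split by stage. By-patient listings of all efficacy endpoints are planned. This narrows the gap without closing it: the joint spleen-and-score rate and the 4.3.7 transfusion summary are not described as investigator-reported, and a listing is not a summary. The layout also keeps treatment-naïve and relapsed/refractory patients apart except in the Overall column, so what is mixed is stages within each group.

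A reader might infer three stronger things that the documents do not support.

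- **That earlier responders already meet the Stage 3A criterion.** Protocol 14.2.1 does report "Fifteen patients (42%) with baseline splenomegaly had spleen responses". Those data are as of July 2021, whereas Stage 3A was added by an amendment dated October 2019 (SAP 1.1.2), so some of these patients may belong to Stage 3A. Nor are they reported as having both a spleen and a symptom response.
- **That earlier CMML patients were never given the questionnaire.** Protocol Table 2, footnote 20, says "Patients with MF should complete the MPN-SAF TSS", and SAP 1.1.3.2 lists no symptom endpoint for Stage 2 CMML. But Protocol section 9 presents that schedule for MF patients enrolled under Amendments 7 and 8. CMML patients enrolled under Amendment 6 or earlier follow the Amendment 6 schedule, which is not supplied.
- **That a go/no-go decision is at risk.** SAP section 5 says that Stage 3A enrolment stopped, Stage 3B will not start, and only descriptive analyses remain. No SAP table is said to apply the one-responder criterion.

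**Conclusion.** The point holds as a mismatch between what was sized and what will be tabulated. As written, SAP 3.5 gives no Stage 3A column to the measurement-based summaries that correspond to the sized outcomes. Protocol 14.2.2 promises an evaluation of each Stage 3A cohort, and SAP section 5 records no departure from that.

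The numerical effect can only be given as a range under assumptions the documents do not settle: 80.3% to 97.2% for at least one responder, or a 15% joint rate shown as low as 6.8%. It is not established that any earlier patient is a joint responder, or that the criterion is already met. The consequence is limited to what the clinical study report can say about Stage 3A. That still matters, because descriptive tables are the only analysis left, and the change should be made before they are produced.

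**What to change.** In SAP 3.5, extend the existing column set (Stages 1-2 and Stage 3A, each split into Treatment Naïve, Relapsed/Refractory and Overall) to the CMML summaries in 4.3.5, 4.3.6 and 4.3.7. Within Stage 3A, report:

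- the joint spleen-and-score rate in patients whose spleen was at least 5 cm below the left costal margin at baseline;
- transfusion conversion in patients who were transfusion-dependent at baseline.

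Give each rate its Clopper-Pearson interval, as SAP 3.2 already provides. Base any statement about the at-least-one-responder criterion on the Stage 3A cohort columns only. A column combining the stages can stay as supportive.

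The cost is low: no new data, and headers the SAP already defines. The drawback is small cells, possibly smaller than the planned 8 to 10 because enrolment stopped, with intervals at least as wide as those shown for 1 of 10 and 1 of 8.
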